## 990 **6.2.2 Reportable Adverse Events**

991 For this protocol, a reportable adverse event includes any untoward medical occurrence that  
992 meets one of the following criteria:

- 993 1. An ADE as defined in section 6.2.1, unless excluded from reporting in section 8.3
- 994 2. An AE as defined in section 6.2.1 occurring in association with a study procedure
- 995 3. An AE as defined in section 6.2.1 that affects the participant's ability to complete any
- 996 study procedures
- 997 4. Hypoglycemia meeting the definition of severe hypoglycemia as defined below
- 998 5. Diabetic ketoacidosis (DKA) as defined below or in the absence of DKA, hyperglycemia
- 999 or ketosis event meeting the criteria defined below.

1000 Hypoglycemia and hyperglycemia not meeting the criteria below will not be recorded as adverse  
1001 events unless associated with an Adverse Device Effect. Skin reactions from sensor placement  
1002 are only reportable if severe and/or required treatment.

1003 All reportable AEs—whether volunteered by the participant, discovered by study personnel  
1004 during questioning, or detected through physical examination, laboratory test, or other means—  
1005 will be reported on an AE form. Each AE form will be reviewed by the Medical Monitor to  
1006 assess for safety and study continuation.

1007      **6.2.3 Hypoglycemic Events**

1008 Hypoglycemia not associated with an Adverse Device Effect is only reportable as an Adverse  
1009 Event when either of the following parameters are met:

1010      ▪ The episode is associated with acute severe cognitive impairment, including incoherence,  
1011      disorientation, and/or combativeness, seizure, or loss of consciousness. Note: If plasma  
1012      glucose measurements are not available during such an event, neurological recovery  
1013      attributable to the restoration of plasma glucose to normal is considered sufficient  
1014      evidence that the event was induced by a low plasma glucose concentration.  
1015      ▪ Capillary glucose is <40 mg/dL

1016 When a hypoglycemic event meets the above reporting requirements, a Hypoglycemia Form  
1017 should be completed in addition to the Adverse Event Form. Severe hypoglycemia events should  
1018 be considered to be serious adverse events with respect to reporting requirements.

1019      **6.2.4 Hyperglycemic/Ketotic Events**

1020 Hyperglycemia not associated with an Adverse Device Effect is only reportable as an Adverse  

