1107 medical care for an adverse event after their participation in the study ends.

1108 **6.3 Reportable Device Issues**

1109 All UADEs and ADEs as defined in section 6.2.1 will be reported on both a device issue form  
1110 and AE form, except for skin reactions from CGM sensor placement or pump infusion set  
1111 placement that do not require pharmacologic treatment. As noted in section 6.2.1, events that  
1112 occur due to user error generally will not require completion of a device issue form.

1113 Device complaints and device malfunctions will be reported except in the following  
1114 circumstances. These occurrences are expected and will not be reported on a Device Issue Form  
1115 assuming criteria for a UADE or ADE have not been met:

- 1116     ▪ CGM sensor lasting fewer days than expected per manufacturer
- 1117     ▪ CGM tape adherence issues

1118 ▪ Battery lifespan deficiency due to inadequate charging or extensive wireless communication  
1119 ▪ Intermittent device component disconnections/communication failures not requiring system  
1120 replacement or workaround/resolution not specified in user guide/manual.  
1121 ▪ Device issues clearly addressed in the user guide manual that do not require additional  
1122 troubleshooting

1123 **6.4 Timing of Event Reporting**

1124 SAEs possibly related to a study device or study participation and UADEs must be reported to  
1125 the Coordinating Site (Emory University) within 24 hours of the site becoming aware of the  
1126 event. This can occur via phone or email, or by completion of the online serious adverse event  
1127 form and device issue form if applicable. If the form is not initially completed, it should be  
1128 completed as soon as possible after there is sufficient information to evaluate the event. All other  
1129 reportable ADEs and other reportable AEs should be submitted by completion on the on-line  
1130 form within 7 days of the site becoming aware of the event.

1131 The Coordinating Site will notify all participating investigators of any adverse event that is  
1132 serious, related, and unexpected. Notification will be made within 10 working days after the  
1133 Coordinating Site becomes aware of the event.

1134 Each principal investigator is responsible for reporting serious study-related adverse events and  
1135 abiding by any other reporting requirements specific to his/her Institutional Review Board or  

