1136 Ethics Committee. Where the JCHR IRB is the overseeing IRB, sites must report all serious,  
1137 related adverse events within seven calendar days.

1138 Upon receipt of a qualifying event, the Sponsor will investigate the event to determine if a  
1139 UADE is confirmed, and if indicated, report the results of the investigation to all overseeing  
1140 IRBs, and the FDA within 10 working days of the Sponsor becoming aware of the UADE per  
1141 21CFR 812.46(b) (2). The Medical Monitor must determine if the UADE presents an  
1142 unreasonable risk to participants. If so, the Medical Monitor must ensure that all investigations,  
1143 or parts of investigations presenting that risk, are terminated as soon as possible but no later than  
1144 5 working days after the Medical Monitor makes this determination and no later than 15 working  
1145 days after first receipt notice of the UADE.

1146 Device malfunctions will be handled by the Sponsor or designee as described below. In the case  
1147 of a device malfunction, information will be forwarded to Insulet by the study staff to be  
1148 addressed by approved company personnel.

1149 **6.5 Safety Oversight**

1150 The study Medical Monitor will review all adverse events and adverse device events that are  
1151 reported during the study. Severe adverse events (SAE) typically will be reviewed within 24  
1152 hours of reporting. Other AEs typically will be reviewed on a weekly basis. Additionally, the  
1153 Medical Monitor will review compiled safety data at the end of phase 1 (n=9) and phase 2 (n=9).

1154

1155 **Safety parameter review:** assessment for any of the below attributed to sensor error or  
1156 inappropriate insulin delivery by the AID system will be reviewed in aggregate after each phase.

1157     ▪ Severe hypoglycemia is defined as severe if the event required assistance of another  
1158        person to actively administer carbohydrate, glucagon, or other resuscitative actions due to  
1159        altered consciousness.

1160     ▪ UADE: means any serious adverse effect on health or safety or any life-threatening  
1161        problem or death caused by, or associated with, a device, if that effect, problem, or death  
1162        was not previously identified in nature, severity, or degree of incidence in the  
1163        investigational plan or application (including a supplementary plan or application), or any  

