## 1174 **6.6 Stopping Criteria**

### 1175 **6.6.1 Participant Discontinuation of Study Device**

1176 In the case of an unanticipated system malfunction resulting in a severe hypoglycemia or DKA  
1177 event (or a malfunction that could have led to severe hypoglycemia or DKA), use of the HCL  
1178 system will be suspended while the problem is diagnosed. The UADE will be reported to the  
1179 IRB and the FDA. After assessment of the problem and any correction, use of the system will not  
1180 be restarted until approval is received from the IRB and the FDA.

1181 HCL therapy will be discontinued and patients will be transitioned to standard subcutaneous  
1182 insulin therapy with continued management by the primary medical/surgical team or inpatient  
1183 endocrine consult service (as clinically warranted) if any of the following occur:

1184     ▪ The investigator believes it is unsafe for the participant to continue on the intervention.  
1185        This could be due to the development of a new medical condition or worsening of an  
1186        existing condition; or participant behavior contrary to the indications for use of the device  
1187        that imposes on the participant's safety

1188     ▪ Participant's clinical team feels transition to IV insulin infusion or MDI regimen is  
1189        necessary for glycemic control

1190     ■ A successful CGM validation has not been achieved per the protocol detailed in section  
1191        3.1.1 on two consecutive CGM sensors  
1192     ■ The participant requests that the treatment be stopped  
1193     ■ Participant pregnancy  
1194     ■ Participant requires hemodialysis or continuous renal replacement therapy (CRRT)  
1195     ■ Participant requires treatment with hydroxyurea or high dose ascorbic acid  
1196     ■ One episode of DKA as defined in section 6.2.4  
1197     ■ One episode of severe hypoglycemia as defined in section 6.2.3  
1198     ■ One episode of DKA as defined in section 6.2.4 and one severe hypoglycemia event as  
1199        defined in section 6.2.3  
1200     ■ Participant is anticipated to be discharged from the hospital without plan to continue  
1201        HCL insulin therapy in outpatient setting; transition to subcutaneous insulin regimen will  
1202        be initiated prior to discharge.

1203     Transfers to the ICU will prompt discontinuation of use of the HCL component of the system  

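### Severe hypoglycemia is judged by conflicting criteria: a capillary glucose below 40 mg/dL in an alert participant counts under 6.2.3 but not under 6.5 or the synopsis

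*Combined protocol and SAP*

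**What the plan says.** **Severe hypoglycemia**

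- 6.2.2 item 4 lists among reportable adverse events "Hypoglycemia meeting the definition of severe hypoglycemia as defined below".
- 6.2.3 is the section that follows. It opens "Hypoglycemia not associated with an Adverse Device Effect is only reportable as an Adverse" Event when either of two criteria is met. The first is acute severe cognitive impairment, including seizure or loss of consciousness. The second is "Capillary glucose is <40 mg/dL". Neither is labelled severe. The section then says that severe events should "be considered to be serious adverse events with respect to reporting requirements".
- 6.6.1 ends closed-loop therapy for a participant after "One episode of severe hypoglycemia as defined in section 6.2.3".
- 6.5, in the list reviewed in aggregate after each phase, says "Severe hypoglycemia is defined as severe if the event required assistance of another" person because of altered consciousness. It has no glucose criterion.
- The synopsis uses the assistance wording for its key safety outcome but labels the outcome reportable, not severe, hypoglycemia. It explains the wording as cognitive impairment up to seizure or coma.
- 8.8 counts severe hypoglycemic events by reference to the protocol's definition and names no section.

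**Reporting and adjudication**

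- 6.4: "SAEs possibly related to a study device or study participation and UADEs must be reported to" the coordinating site within 24 hours. Other reportable events have 7 days.
- 6.2.2 provides that "Each AE form will be reviewed by the Medical Monitor to" assess safety and study continuation. 6.2.8 gives the Medical Monitor the final decision on causality and seriousness.

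**Study hold**

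- 6.6.2 holds the whole study for any of (a) adverse events attributable to the study device, with DKA and seizure named as included, or (b) two patients who each have at least one severe hypoglycemia episode attributable to insulin the device delivered. 8.13 repeats both as prompts for an interim safety review.

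**The concern.** Severe hypoglycemia drives an individual discontinuation rule, a study-hold trigger, an expedited report, a phase review and a tabulated outcome. If its criteria change with the section consulted, three sites can handle the same event differently in good faith, and a reader of the final table cannot tell what was counted. This matters because 1.4.1.1 says the system's glucose target is below what most hospitals use and that hypoglycemia risk may be greater as a result, and because the results are meant to inform a larger randomized trial.

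The hold rule adds a second difficulty. Trigger (b) waits for two patients, while trigger (a) has no count and no seriousness limit, so the text leaves open whether (b) was meant to have effect.

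**Working it through.** **Step 1. The definitions side by side.** Use three features of an event: capillary glucose <40 mg/dL (G), severe cognitive impairment (C), and another person's assistance needed for altered consciousness (A). Read as the definition, 6.2.3 is met if G or C holds; 6.5 is met if A holds.

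| G | C | A | 6.2.3 | 6.5 |
|---|---|---|---|---|
| no | no | no | no | no |
| no | no | yes | no | yes |
| no | yes | no | yes | no |
| no | yes | yes | yes | yes |
| yes | no | no | yes | no |
| yes | no | yes | yes | yes |
| yes | yes | no | yes | no |
| yes | yes | yes | yes | yes |

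The two disagree in 4 of 8 rows. Three of those four have C without A or A without C. These should be rare, because the synopsis explains the assistance test in terms close to the first 6.2.3 criterion. The row that matters is G alone: an alert participant below 40 mg/dL.

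**Step 2. What each reading does to that participant.**

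- *The 6.2.3 list is the definition, as 6.6.1 says.* The discontinuation rule applies, and the site handles the event as serious (24 hours under 6.4 if possibly related to the device or participation). It is still not severe hypoglycemia under 6.5.
- *Severe is only a subset of the 6.2.3 list.* The event is reportable within 7 days unless judged serious on other grounds. But then 6.2.2 item 4 and 6.6.1 cite a definition that 6.2.3 does not contain.

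On either reading, 6.2.3 makes this event reportable, while the synopsis definition of reportable hypoglycemia excludes it. 8.8 does not choose. Its separate line for events with seizure or loss of consciousness shows that the main count is wider than those, but not whether G alone counts. In addition, 6.2.3 is worded for hypoglycemia *not* associated with an adverse device effect, so it does not clearly define severity for device-associated events, which are the ones relevant to the hold. DKA shows no such split: 6.2.4 and 6.5 agree.

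**Step 3. The hold triggers.** Read literally, a single severe hypoglycemia event attributable to device-delivered insulin is ordinarily also an adverse event attributable to the device, so (a) is met at the first patient. A possible exception is a user-error bolus that the device delivered correctly: staff give boluses through the system (3.1.2), and 6.2.1 generally does not treat pure user error as an adverse device effect. Literal (a) would also take in a reportable skin reaction to the device, a kind of event listed as a known risk in 1.4.1.2. The words naming DKA and seizure may therefore have been meant as a limit; the text does not say.

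**Step 4. Size, on assumed rates.** The documents give no event rates and no operating characteristics for the hold, so there is no plan figure to reproduce. Take p as an assumed per-participant probability, with participants independent; n=18 is the target and n=30 the enrollment cap (8.3).

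*Counts differ.* Let p be the chance of at least one G-alone event, and set aside the rare C/A mismatches. The 6.2.3 and 6.5 counts differ if any such event occurs: P = 1 − (1 − p)^n. At p=2%, n=18: 1 − 0.98^18 = 1 − 0.695 = 0.305.

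| p | n=18 | n=30 |
|---|---|---|
| 1% | 0.165 | 0.260 |
| 2% | 0.305 | 0.455 |
| 5% | 0.603 | 0.785 |

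*Hold at one patient versus two.* Let p be the chance of device-attributable severe hypoglycemia, and ignore all other device events. P(≥2) = 1 − (1 − p)^n − np(1 − p)^(n−1). At p=2%, n=18: 1 − 0.695 − 0.255 = 0.050.

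| p | n=18: one vs two | n=30: one vs two |
|---|---|---|
| 2% | 0.305 vs 0.050 | 0.455 vs 0.121 |
| 5% | 0.603 vs 0.226 | 0.785 vs 0.446 |

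**Step 5. A smaller cross-reference gap.** 6.2.2 item 5 makes hyperglycemia or ketosis without DKA reportable under criteria said to follow. 6.2.4 gives DKA criteria only and, without an adverse device effect, limits reporting to DKA.

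**The case against.** The strongest reply is that little turns on this. The Medical Monitor reviews every adverse event form and the compiled data after each phase, and under 6.2.8 has the last word on seriousness. Apart from the glucose criterion, the synopsis and 6.2.3 describe nearly the same event. The literal hold reading is the more cautious one. The study is an unpowered, descriptive pilot that lists values for each patient, and every rate used above is assumed.

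Much of this stands. It confines the conflict to the <40 mg/dL criterion and removes any claim that sites would end with different final seriousness classifications. It does not settle whether 6.6.1 applies at the bedside, which reporting clock the site starts, or what the 8.8 line contains.

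Three stronger inferences are tempting and are not supported:

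- *Severe events could go unseen.* 6.2.3 makes the alert <40 mg/dL event reportable on either reading, and each reported event reaches the Medical Monitor.
- *A hold could be missed.* The literal text of trigger (a) holds earlier, not later. Separately, 6.6.1 already suspends use after an unanticipated malfunction that caused, or could have caused, severe hypoglycemia or DKA, and 6.6.2 adds its triggers to that.
- *The two-patient trigger can never operate.* The user-error case leaves it some room. It has little effect, which is not the same as none.

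**Conclusion.** The point holds as an internal inconsistency that should be fixed. For an alert participant with capillary glucose below 40 mg/dL, the section consulted determines whether the 6.6.1 rule applies, the site's first reporting route, and whether the event is severe hypoglycemia in the 6.5 review and the 8.8 count. The harm is possible inconsistent handling across three sites and a safety count whose definition is not stated. This conclusion is textual and needs no rate; the probabilities only show that, at assumed rates of 1% to 5%, the counts could plausibly diverge even in a study of 18.

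The overlap of the hold triggers is a secondary redundancy that leaves the intended threshold unclear and errs toward more review. The missing non-DKA criteria are a minor clarification. Confidence is high on the mismatch of definitions and lower on what the hold triggers were meant to say.

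**What to change.** The sponsor's clinicians should reconcile the synopsis, 6.2.2 to 6.2.4, 6.5, 6.6.1, 6.6.2, 8.8 and 8.13, so that there is:

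- one definition of severe hypoglycemia, stated to cover events associated with an adverse device effect, and one use of the term reportable;
- one stated reading of the two hold triggers;
- one statement on whether, and by what criteria, hyperglycemia or ketosis without DKA is reportable.

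No view is taken here on which definition or hold rule is right.

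In 8.8, name the section that defines the count and tabulate separately (i) events with severe cognitive impairment or altered consciousness and (ii) events with capillary glucose <40 mg/dL without either. Readers can then recover the count under either definition.

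The cost is a wording amendment and one or two table lines. It needs no new data collection provided that the Hypoglycemia and Adverse Event Forms record consciousness and assistance, and that they are completed for device-associated events. The form contents are not in the documents, so this should be checked.

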1021 Event if the event involved DKA. Hyperglycemic events are classified as DKA if the following  
1022 are present:

1023      ▪ Symptoms such as polyuria, polydipsia, nausea, or vomiting;  
1024      ▪ Serum ketones >1.5 mmol/L or large/moderate urine ketones;  
1025      ▪ Either arterial blood pH <7.30, venous pH <7.24, or serum bicarbonate (or CO2) <15  
1026      mEq/L  
1027      ▪ DKA is suspected as either the primary or a contributing cause for these findings

1028 When a hyperglycemia/ketotic event meets the above reporting requirements, an Adverse  
1029 Event Form should be completed. Events meeting DKA criteria should be considered  
1030 serious adverse events with respect to reporting requirements. Hyperglycemia events not  
1031 meeting criteria for DKA generally will not be considered as serious adverse events  
1032 unless one of the SAE criteria in section 6.2.1 is met.

1033      **6.2.5 Relationship of Adverse Event to Study Investigational Device**

1034 The study investigator will assess the relationship of any adverse event to be related or unrelated  
1035 by determining if there is a reasonable possibility that the adverse event may have been caused  
1036 by the study device.

1037 To ensure consistency of adverse event causality assessments, investigators should apply the  
1038 following general guideline when determining whether an adverse event is related:

1039      ▪ **Unrelated:** The AE is clearly not related to a study drug/device and a likely alternative  
1040      etiology exists such as an underlying disease, environmental or toxic factors or other therapy.

- 1041   ■ **Unlikely Related:** The AE does not follow a reasonable temporal sequence during or after  
1042   use of study drug/device and a more likely alternative etiology exists such as an underlying  
1043   disease, environmental or toxic factors, or other therapy.
- 1044   ■ **Possibly Related:** The AE occurred in a reasonable time during or after use of study  
1045   drug/device; but could be related to another factor such as an underlying disease,  
1046   environmental or toxic factors, or other therapy; and there is a possible, though weak,  
1047   scientific basis for establishing a causal association between the AE and the study  
1048   drug/device.
- 1049   ■ **Probably Related:** The AE occurred in a reasonable time during or after use of study  

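### Section 6.2.2 makes non-DKA hyperglycemia reportable under criteria that section 6.2.4 never gives, leaving a narrow gap in which a serious event could go without an AE form

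*Combined protocol and SAP*

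**What the plan says.** Section 6.2.2 lists five kinds of reportable adverse event. Item 5 covers DKA and, where DKA is absent, a hyperglycemia "or ketosis event meeting the criteria defined below". After the list comes an exclusion: "Hypoglycemia and hyperglycemia not meeting the criteria below will not be recorded as adverse" events, the one exception being association with an ADE.

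Section 6.2.4 is where the hyperglycemia criteria should be. It opens "Hyperglycemia not associated with an Adverse Device Effect is only reportable as an Adverse" and continues "Event if the event involved DKA". It then sets out the DKA criteria and no others. It closes by saying that non-DKA hyperglycemia will generally not count as serious "unless one of the SAE criteria in section 6.2.1 is met".

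Two general items in 6.2.2 could also apply. Item 2 is "An AE as defined in section 6.2.1 occurring in association with a study procedure". Item 3 is "An AE as defined in section 6.2.1 that affects the participant's ability to complete any" study procedures.

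Review depends on the form ("Each AE form will be reviewed by the Medical Monitor to" assess safety and continuation). Section 6.2.8 gives the Medical Monitor the last word on causality and seriousness.

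The eligibility criteria (Protocol Summary, Overview of Study Design, section 2.3.2) name hyperosmolar hyperglycemic state together with DKA as a hyperglycemic crisis. It is not named in 6.2.4, in the 6.5 safety review list, in the ICU-transfer sentence of 6.6.1 or in the 8.8 tabulation.

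**The concern.** The second half of item 5 refers to criteria that are not in the protocol. The two exclusion sentences then turn that omission into a rule: without DKA and without an ADE, hyperglycemia is not recorded. The same section allows that such an event can be serious. An event could therefore meet an SAE criterion in 6.2.1 and still have no stated place on an AE form.

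This matters because of who makes the decision. If the exclusion sentences are followed, the site's attribution determines whether a form exists, and the form is what brings that attribution to the Medical Monitor. The judgment that most needs a second look would be the one that does not get it. The three sites could also resolve the unclear wording differently, so that the same event is counted at one and not at another.

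**Working it through.** The documents give no rate for such events and no arithmetic applies, so the check is to follow one event through the text. Take a hyperglycemic event, for example a hyperosmolar state, that meets a 6.2.1 SAE criterion but lacks the ketone and acidosis findings required for DKA.

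1. **Item 5 of 6.2.2.** It is not DKA, so only the second half could apply. That half needs criteria from later in the section. 6.2.4 gives none for non-DKA events, so item 5 does not capture it.
2. **Item 1 (ADE).** Section 6.2.1 defines an ADE as an occurrence that the device may have caused or contributed to. This is a low threshold, and most events during active closed-loop use should meet it. If the site judges it met, an AE form and Medical Monitor review follow. The rest of the check assumes that it does not.
3. **Items 2 and 3.** A crisis that ends closed-loop use could fit item 3, and an event tied to a study procedure could fit item 2. The exclusion sentence comes after the list and refers to criteria further down, that is, to 6.2.3 and 6.2.4. Read literally it removes hyperglycemia even where item 2 or 3 would include it. No precedence is stated.
4. **The closing clause of 6.2.4.** It concerns whether an event is serious, not whether it is reportable. It can be read as applying only to hyperglycemia already reportable through an ADE, so it is not a separate route to a form.
5. **Sections 6.4 and 6.5.** An SAE possibly related to the device or to study participation goes to the Coordinating Site within 24 hours, and the Medical Monitor typically reviews it within 24 hours of reporting. This route does not depend on the 6.2.2 list. It does depend on the site judging the event possibly related.
6. **What remains.** The event must be judged unrelated both to the device and to study participation, and the site must let the exclusion sentence override items 2 and 3. Then there is no AE form.

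Effect on the 12 rows of 8.8 in that case: the event is missing from the rows for AEs, participants with an AE, SAEs and participants with an SAE. If treatment was stopped, it is also missing from the row for stopping in response to an AE. The only row naming a hyperglycemic crisis is the DKA row, which does not apply. The ICU-transfer row would count a transfer but carries no causality review. This describes the consequence of a missing form. It does not say how often a form would be missing.

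**The case against.** The strongest reply is that the text is incomplete rather than contradictory. Item 5 is conditional. With no non-DKA criteria supplied, its second half is empty, and the two exclusion sentences state one consistent rule. That is a fair reading, and a flat contradiction between 6.2.2 and 6.2.4 should not be inferred. It leaves the rule itself in place: a serious event can be excluded from AE recording by attribution alone.

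A second reply is that the event would surface elsewhere. Section 6.1 sends possibly research-related unanticipated problems to the Medical Monitor within seven days. Section 7.2 records medical conditions that could affect protocol conduct or an outcome assessment. Section 8.9 collects reasons for discontinuation, and 8.8 counts ICU transfers. These stand, and they make the gap small. But 6.1, like 6.4, requires a judgment of possible relation, and the other three do not bring the site's attribution to the Medical Monitor.

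A reader might also infer that events due solely to user error escape, because 6.2.1 generally does not class them as ADEs. The documents do not support giving this weight. Patients do not operate the system (section 3.1). An error by trained staff plausibly falls under item 2 and under study participation in 6.4, and 6.2.1 itself notes that such an event may still be reportable.

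Finally, limiting AE reporting to listed events is the sponsor's choice. That is accepted. The point concerns only serious events and a reference that leads nowhere.

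**Conclusion.** The point holds as a minor safety-reporting correction. Item 5 refers to criteria that are never given. Read literally, the exclusion wording lets a serious non-DKA hyperglycemic event go without an AE form if the site judges it unrelated to the device and to study participation. In that case the Medical Monitor does not review the attribution, and the AE and SAE counts in 8.8 omit the event.

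A reader might go further and infer that a hyperosmolar crisis would generally escape oversight in this trial. The documents do not support that, given the broad ADE definition and the 6.4 and 6.5 route. Nor does the ICU-transfer sentence in 6.6.1 establish it. That sentence says when a transfer is itself an AE or ADE, not that the underlying event goes unreported.

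The conclusion rests on two assumptions: that sites follow the specific exclusion wording over the general items, and that such an event can occur and be judged unrelated. No probability can be attached to either from the documents.

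**What to change.** - Reconcile item 5 and the exclusion sentence of 6.2.2 with 6.2.4, 6.4 and the ICU-transfer parenthesis in 6.6.1, and say how the exclusion relates to items 2 and 3.
- Either supply the non-DKA hyperglycemia or ketosis criteria that item 5 mentions, or delete the reference. Their content is for the sponsor to set.
- State that any hyperglycemia event meeting a 6.2.1 SAE criterion is recorded on an AE form whatever the site's device attribution. It then reaches the Medical Monitor and enters the existing AE and SAE rows of 8.8.
- Optionally, add a separate 8.8 row for hyperosmolar hyperglycemic state beside DKA.

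The cost is a few sentences of protocol wording and slightly more AE reporting. No new test or analysis is needed, and the discontinuation and study-hold rules need not change for this purpose.
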